7.2. Setting

7.2.1. Inclusion criteria

Patients must meet all of the following inclusion criteria to be eligible for inclusion in the study:

1. Patients with active RA who start treatment with Enbrel according to the prevailing reimbursement criteria in Belgium and dosing in line with the SmPC.
 - a) First cohort: Enbrel is the first biological product prescribed.
 - b) Second cohort: Enbrel is the second biological product prescribed.
2. Capable of understanding and willing to provide signed and dated written, voluntary informed consent before any protocol-specific procedures are performed.
3. Eighteen (18) years of age or older at time of consent.
4. Evidence of a personally signed and dated informed consent document indicating that the patient (or a legally acceptable representative) has been informed of all pertinent aspects of the study.

7.2.2. Exclusion criteria

Patients meeting any of the following criteria will not be included in the study:

1. History of or current psychiatric illness that would interfere with the subject's ability to comply with protocol requirements or to give informed consent.

7.3. Variables

Table 2. Variables, roles, data sources and operational definitions

Variable	Role	Data source(s)	Operational definition
Demographics	Baseline variables	Medical records	Please refer to the SAP*
Disease duration	Baseline variables	Medical records	Please refer to the SAP*
Cohort 1 or 2	Sub-group identifier	Medical records	Please refer to the SAP*
DAS28	Outcome variable	Medical records	Please refer to the SAP*
SDAI	Outcome variable	Medical records	Please refer to the SAP*
CDAI	Outcome variable	Medical records	Please refer to the SAP*
BOOLEAN CDAI SJC \leq 1, TJC \leq 1, PtGA \leq 1	Outcome variable	Medical records	Please refer to the SAP*
BOOLEAN SDAI SJC \leq 1, TJC \leq 1, PtGA \leq 1 and CRP \leq 1	Outcome variable	Medical records	Please refer to the SAP*

Variable	Role	Data source(s)	Operational definition
Ultrasound (Selected Centers)	Outcome variable	Medical records	Please refer to the SAP*
HAQ	Outcome variable	Medical records	Please refer to the SAP*
Current medication	Exposure	Medical records	Please refer to the SAP*
Adverse events	Safety	Medical records	Please refer to the SAP*

* SAP = Statistical Analysis Plan

7.4. Data sources

This study will be a primary data collection study. The data source will be the medical records for all variables. For all details please refer to the Statistical Analysis Plan (SAP).

7.5. Study size

It will not be possible to justify the sample size of the study on the basis of inferential statistical assumptions. Indeed, there are currently insufficient data available concerning the prediction of remission on the basis of CDAI, SDAI, DAS28, DAS28 and Ultrasound, and EULAR Boolean definition for clinical practice and clinical studies.

The analysis of the primary endpoint will be based on a logistic regression defining the dependent variable as the remission at Month 12 and the 5 independent variables as CDAI, SDAI, DAS28, DAS28 and Ultrasound, and EULAR Boolean definition for clinical practice and clinical studies.

This analysis will be conducted in each arm of the study if possible as well as after pooling of both patient groups.

In this context it seems reasonable to ensure the completion of the study by a total approximate number of 100 patients (approximately 50 patients per arm). In order to ensure 50 completers in each arm, 70 patients will be recruited at baseline, taking into account a drop out rate of 30% over 1 year period. In order to have 100 evaluable patients for the predictive model and given the current recruitment status (January 26th 2015 RA 1st: 34 vs RA 2nd: 4) we will allow the needed number of patients to be recruited in whichever cohort: 1st or 2nd. This will limit the potential extension of the recruitment period.

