3. AMENDMENTS AND UPDATES

On January 26, 2015, the recruitment status was as follows: 34 patients included in the cohort 1st biological versus 4 in the cohort 2nd biological.

For our predictive model, we need 100 evaluable patients but the cohort in which the patients are recruited will not impact the results.

In order to have 100 evaluable patients for the predictive model and given the above mentioned recruitment status, we decided to amend the protocol to allow the needed number of patients to be recruited in whichever cohort: 1st or 2nd. This will limit the potential extension of the recruitment period. [REDACTED]

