4. MILESTONES

Milestone	Planned date
Completion of feasibility assessment	30 June 2014
Start of data collection	15 July 2014
End of data collection	30 June 2016
Interim report 1	30 January 2017
Final study report	31 May 2017

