7.7. Data analysis

Detailed methodology for summary and statistical analyses of data collected in this study will be documented in a SAP, which will be dated, filed and maintained by the sponsor. The SAP may modify the plans outlined in the protocol; any major modifications of primary endpoint definitions or their analyses would be reflected in a protocol amendment.

The analysis of the primary endpoint will be based on a logistic regression defining the dependent variable as the remission at month 12 and the 5 independent variables as CDAI, SDAI, DAS28, DAS28 and Ultrasound, and EULAR Boolean definition for clinical practice and clinical studies. This analysis will be conducted in each arm of the study as well as after a pooling of both patient groups.

The other statistical methods used for the analysis of the data will be mainly descriptive.

Appropriate inferential analyses will be used to compare the over-time modifications of study parameters and potentially to compare the two arms of the study.

Time to event variables will be analyzed using the Kaplan-Meier's method with comparison between groups being ensured by the log rank test.

An interim analysis of baseline data will be performed at Month 6.

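### The amended target of 100 evaluable patients at Month 12 does not fit a calendar that still ends data collection on 30 June 2016

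*Combined protocol and SAP*

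**What the plan says.** Section 4 lists planned dates: "Start of data collection 15 July 2014", "End of data collection 30 June 2016" and "Final study report 31 May 2017". It gives no end-of-recruitment date.

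Section 3 records, on 26 January 2015, "34 patients included in the cohort 1st biological versus 4 in the cohort 2nd biological". It also states: "For our predictive model, we need 100 evaluable patients but the cohort in which the patients are recruited will not impact the results".

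Section 7.5 repeats the recruitment status and says that "given the current recruitment status (January 26th 2015 RA 1st: 34 vs RA 2nd: 4) we will allow the needed number of patients" to come from either cohort. Its size rests on about 50 completers per arm, 70 recruited and 30% lost over one year. It says openly that no inferential justification is possible. Sections 3 and 7.5 both add that freeing the cohort mix should limit a possible lengthening of recruitment. Neither gives a new date in its legible text. In section 3 a redaction follows that sentence.

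The primary outcome is remission at Month 12 (sections 6.1, 7.5 and 7.7). Table 1 allows that visit between Months 11 and 13.

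**The concern.** With a fixed end of data collection, the period in which enrolment helps the primary objective closes about a year earlier, however long recruitment continues. The amended text changes which cohort a patient may enter. It does not change the date by which that patient must be observed, although it accepts that recruitment may run longer. On 26 January 2015 fewer than four in ten of the 100 patients had been enrolled, before any drop-out, and five to six useful months remained.

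At stake is the amount of data for the primary logistic regression, which relates remission at Month 12 to five overlapping criteria at Month 6. Patients enrolled after mid-2015 could still contribute to the descriptive objectives at earlier visits, but not to the Month 12 prediction. The 100 is the plan's only statement of the size that it needs.

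**Working it through.** **Inputs.** Start 15 July 2014, end 30 June 2016 and final report 31 May 2017 (section 4). Enrolled by 26 January 2015: 34 + 4 = 38 (sections 3 and 7.5). Need: 100 evaluable (section 3). Drop-out: 30% (section 7.5). Month 12 window: Months 11 to 13 (Table 1).

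**1. The plan's own figure.** 50 / 0.7 = 71.4, or 72 per arm, against 70 stated; conversely 70 × 0.7 = 49. In total 100 / 0.7 = 143, against 2 × 70 = 140, and 140 × 0.7 = 98. Given the plan's approximate wording, 70 per arm reproduces. Reading 70 as the total would leave only 49 completers, so per arm is the reading that fits 100 evaluable.

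**2. Last useful enrolment date.** Counting back from 30 June 2016 gives 30 June 2015 for a visit at exactly 12 months, 31 July 2015 for the earliest permitted visit (Month 11) and 30 May 2015 for the latest (Month 13). From 26 January 2015 these leave 155, 186 and 124 days.

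**3. Base-case rate (assumption).** Suppose enrolment began on the planned date and was constant. From 15 July 2014 to 26 January 2015 is 195 days, and 38 / 195 = 0.195 per day, or 5.9 per month.

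**4. Projection.** Enrolled = 38 + rate × days left; evaluable = 0.7 × enrolled.
- 30 June 2015: 38 + 0.1949 × 155 = 68.2, giving 47.7.
- 31 July 2015: 38 + 0.1949 × 186 = 74.2, giving 52.0.
- 30 May 2015: 38 + 0.1949 × 124 = 62.2, giving 43.5.
- With no drop-out at all, the first two give 68 and 74.

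**5. Sensitivity, one assumption at a time.** The 95% Poisson limits on a count of 38 are 26.9 and 52.2; they are applied to future accrual only.

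| Assumption | Enrolled by 30 June / 31 July 2015 | Evaluable |
|---|---|---|
| Base case | 68.2 / 74.2 | 47.7 / 52.0 |
| Lower Poisson limit | 59.4 / 63.6 | 41.6 / 44.6 |
| Upper Poisson limit | 79.5 / 87.8 | 55.6 / 61.4 |
| Actual start 1 September 2014 | 78.1 / 86.1 | 54.6 / 60.3 |
| Actual start 1 October 2014 | 88.3 / 98.4 | 61.8 / 68.9 |
| Actual start 1 November 2014 | 106.5 / 120.2 | 74.5 / 84.1 |
| Twice the base-case rate | 98.4 / 110.5 | 68.9 / 77.3 |

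The overall span is roughly 42 to 84. Favourable extremes can be stacked. A 1 November start (86 days to 26 January) with the upper Poisson limit gives 0.7 × (38 + 52.2 / 86 × 155) = 92.5 for a 12-month visit and 0.7 × (38 + 52.2 / 86 × 186) = 105.6 for a Month 11 visit. Only the last of these passes 100.

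**6. What the target would require.** For 140 recruits, 102 more are needed. The multiple of the base-case rate is 102 / (155 × 0.1949) = 3.4, or 102 / (186 × 0.1949) = 2.8. Equivalently, constant accrual meets 140 to 143 recruits in time only if enrolment really began between about 18 November and 1 December 2014.

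**7. Effect of freeing the cohort mix.** In the base case the first cohort enrols 34 / 195 per day and reaches 70 after 70 / (34 / 195) = 401 days, about 20 August 2015. That is after both cut-offs, so a limit of 70 per cohort was not what held back useful enrolment.

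**8. If recruitment simply continues.** In the base case the 140th patient enters 102 / 0.1949 = 523 days after 26 January 2015, about 2 July 2016, and reaches Month 12 about 2 July 2017. Both dates fall after the corresponding milestones.

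**The case against.** The strongest reply is that this is a forecast. The protocol states one count, no rate and no first-enrolment date, and section 4 labels its dates as planned. Sites may have opened late, which would make the true rate higher than 5.9 per month. That stands. It is why 48 to 52 can only be a base case and why the range must be shown.

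Second, the sponsor foresaw that recruitment might be lengthened, and the redaction in section 3 means that section cannot be cited as silent on timing. That also stands. It does not remove the mismatch, because the end of data collection in section 4 is legible and unchanged. Recruiting for longer adds no Month 12 outcomes unless that date moves.

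Third, 100 is a pragmatic number, so no power claim fails. This is correct; the shortfall is against the plan's own stated need.

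Some stronger readings are not supported:
- A reader might infer that the final report would precede the Month 12 visits of the recruits in general. In the base case that is true only of those enrolled after 31 May 2016, about 32 days × 0.195 = 6 patients.
- A reader might infer that late patients will be counted as missing. Nothing in the protocol says how they would be handled.
- A reader might link the sentence "An interim analysis of baseline data will be performed at Month 6" to the interim report dated 30 January 2017 and call the interim too late. The documents do not say that these are the same item or what Month 6 is counted from, so the point is not made here.

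**Conclusion.** The concern holds as an inconsistency between the target, the accrual to date and the calendar. With data collection ending on 30 June 2016, the base case yields about 48 to 52 evaluable patients against 100. The range is roughly 42 to 84 when Poisson error or a later actual start (up to 1 November 2014) is allowed for, each on its own. The base case falls short even with no drop-out (68 to 74). Freeing the cohort mix does not by itself raise overall accrual.

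The result rests on accrual that is constant from an assumed start date and on 30% drop-out applied to everyone enrolled. A reader might take 48 to 52 as a documented ceiling. It is not one, since the documents state no rate and a marked acceleration cannot be excluded. What the documents do show is that the plan neither states nor explains the acceleration that its dates require. No endpoint, model or analysis set is wrong on this account, so the point is a should-fix.

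**What to change.** Reconcile sections 3, 4 and 7.5 in one of two ways.

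(a) Define the end of data collection as the last enrolled patient's Month 12 visit, with the window to Month 13, and re-date the final report to follow it.

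(b) Keep 30 June 2016, state a last-enrolment date that allows the Month 12 visit, and restate the expected evaluable number in sections 3 and 7.5. That number should come from the sponsor's own accrual projection, with the actual first-enrolment date, assumed rate and drop-out shown. The range above is a check on that projection and should not be copied into the protocol.

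Neither option adds procedures or visits. The cost of (a) is a later report; the cost of (b) is a less favourable stated number.

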7.6. Data management

All the data will be recorded by the Investigators and their study nurses in an electronic Case Report Form (eCRF).

The Data Management of the study will be done directly in the eCRF by the automatic generation of inconsistencies and by the manual generation of queries.

The statistical software which will be used for the analyses is the IBM-SPSS Statistics program (Version 21.0 and eventual upgrades/updates).

7.7. Data analysis

Detailed methodology for summary and statistical analyses of data collected in this study will be documented in a SAP, which will be dated, filed and maintained by the sponsor. The SAP may modify the plans outlined in the protocol; any major modifications of primary endpoint definitions or their analyses would be reflected in a protocol amendment.

The analysis of the primary endpoint will be based on a logistic regression defining the dependent variable as the remission at month 12 and the 5 independent variables as CDAI, SDAI, DAS28, DAS28 and Ultrasound, and EULAR Boolean definition for clinical practice and clinical studies. This analysis will be conducted in each arm of the study as well as after a pooling of both patient groups.

The other statistical methods used for the analysis of the data will be mainly descriptive.

Appropriate inferential analyses will be used to compare the over-time modifications of study parameters and potentially to compare the two arms of the study.

Time to event variables will be analyzed using the Kaplan-Meier's method with comparison between groups being ensured by the log rank test.

An interim analysis of baseline data will be performed at Month 6.

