6. RESEARCH QUESTION AND OBJECTIVES

This study aims both to evaluate remission according to different criteria and to look at which remission criterion at Month 6 is the most predictive for remission at Month 12.

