6.1. Primary Objective

To determine which remission criterion at Month 6 predicts remission at Month 12 the best.

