6.2. Secondary Objectives

- Describe the percentage of patients in remission at the different DCPs (Data Collection Points) according to different remission criteria: CDAI, SDAI, DAS28, DAS28 in combination with Ultrasound, EULAR Boolean definition for clinical practice and clinical studies.
- Describe percentage of the same patients in remission at the different DCPs, according to different remission criteria: CDAI, SDAI, DAS28, DAS28 in combination with Ultrasound, EULAR Boolean definition for clinical practice and clinical studies.
- Determine if the quantitative change in between baseline and Month 6 is predictive for the change at Month 12.
- Determine which single component is the most predictive for the composite index of remission.
- Determine predictors for remission, according to all the different criteria at each timepoint.
- Comparison between DAS28 remission and US remission

- Prediction of remission based on US data

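### The plan requires no internal validation of the five-variable predictive model in about 100 patients, so predictive performance reported from those same patients is expected to be overstated.

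*Combined protocol and SAP*

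**What the plan says.** The primary objective (6.1) is: "To determine which remission criterion at Month 6 predicts remission at Month 12 the best". For the analysis, section 7.7 states: "The analysis of the primary endpoint will be based on a logistic regression defining the dependent variable as the remission at month 12", and gives as predictors "the 5 independent variables as CDAI, SDAI, DAS28, DAS28 and Ultrasound, and EULAR Boolean definition for clinical practice and clinical studies". Section 3 says: "For our predictive model, we need 100 evaluable patients". Section 7.5 plans for a "total approximate number of 100 patients (approximately 50 patients per arm") completing the study. The amendment then lets the needed number come from either cohort, because recruitment on 26 January 2015 stood at 34 versus 4.

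The model is to be fitted pooled and in each arm. Section 7.5 makes the by-arm fits conditional on feasibility; section 7.7 does not. Ultrasound, which enters one of the five predictors, is done only in selected centers (7.1). A secondary objective is "Prediction of remission based on US data" (6.2), for which no model is given.

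Section 7.7 describes the remaining methods as largely descriptive. The protocol contains no split sample, external data, cross-validation, bootstrap, shrinkage or penalisation. It names no performance measure and no rule for declaring one criterion the best. Section 7.9 limits its caveats to the observational, uncontrolled design. Detailed methods are left to a separate SAP, whose text is not in the document reviewed.

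**The concern.** There is one dataset and no validation step. Unless the SAP adds one, any statement of how well the Month 6 criteria predict Month 12 remission would come from the patients who supplied the coefficients. On average such figures are better than the same model would achieve in new patients. A confidence interval around the apparent figure does not remove that bias.

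The choice of winner adds a second source. If several criteria are compared in the same data and the best is reported, its apparent performance is expected to be inflated, even when each criterion is a fixed rule.

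At stake is the credibility of the primary result. A reader could take the reported performance as what to expect in practice, and could take the named criterion as more clearly ahead of the others than it is.

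**Working it through.** **1. The plan's own figure.** Section 7.5 gives 50 completers per arm and 30% dropout. 50 / (1 − 0.30) = 71.4, or 72 rounded up, against 70 stated. Conversely, 70 × 0.70 = 49 per arm, or 98 in total. The recruitment figure is therefore reproduced to within two patients per arm. The 100 evaluable patients cannot be derived: section 7.5 gives no error rate, power, effect size or remission rate, and says that no inferential justification is possible.

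**2. Events per predictor.** Formula: n × p / 5, where p is the Month 12 remission rate. The protocol does not give p; 20% to 40% is assumed.

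| n | p = 20% | p = 40% |
|---|---|---|
| 100 (pooled) | 100 × 0.20 / 5 = 4 | 100 × 0.40 / 5 = 8 |
| 50 (one arm as first planned) | 50 × 0.20 / 5 = 2 | 50 × 0.40 / 5 = 4 |

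If the two Boolean definitions are counted separately there are six predictors, and the pooled figures fall to 20 / 6 = 3.3 and 40 / 6 = 6.7.

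**3. Expected optimism.** Optimism is the mean AUC in the fitting sample minus the mean AUC in new patients. Five correlated Month 6 criteria entered a near-unpenalised logistic model. All inputs are assumptions:
- Set A: Month 12 remission 20% to 40%; latent correlation between criteria 0.6 to 0.85; latent Month 6 to Month 12 correlation 0.5 to 0.7; criteria binary or continuous; 300 samples per setting.
- Set B: remission 20% or 35%; Month 6 to Month 12 correlation 0.4 to 0.6; binary criteria with prevalence about 15% to 40%; 600 samples per setting, each model tested in 20,000 new patients.
- Set C: a further simulation under assumed inputs, as a check on A and B.

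| AUC optimism | n=100 | n=50 |
|---|---|---|
| Five-variable model, set A | 0.03–0.08 | 0.06–0.16 |
| Five-variable model, set B | 0.05–0.09 | 0.10–0.17 |
| Five-variable model, set C | 0.04–0.10 | 0.11–0.18 |
| Best single criterion, set A | 0.02–0.06 | – |
| Best single criterion, set C | 0.02–0.05 | – |

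Across the sets, the ranges are 0.03–0.10 (five-variable, n=100), 0.06–0.18 (five-variable, n=50) and 0.02–0.06 (best single criterion, n=100).

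In set A the median calibration slope in new patients was 0.58–0.83 at n=100 and 0.20–0.66 at n=50, so predictions would be too extreme. With no true association, the apparent AUC at n=100 was still 0.61–0.66, against a true value of 0.50.

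**4. One setting in full.** Set A, continuous criteria, correlation between criteria 0.85, Month 6 to Month 12 correlation 0.5, remission 20%, n=100. Five-variable model: 0.782 apparent, 0.713 in new patients, difference 0.069. Best single criterion: 0.766 apparent, 0.726 in new patients, difference about 0.04. The fitted model looks better in the study data (0.782 against 0.766) and is worse in new patients (0.713 against 0.726). Uncorrected figures can therefore mislead on ranking as well as on level.

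**The case against.** The strongest reply is that the objective is comparative. The protocol plans no risk score and names no AUC, Brier score or calibration measure, so that performance would be judged in the same patients is an inference from there being one dataset and no validation step. The Month 6 criteria are also predefined rules. A fixed rule assessed alone has no fitted weights, and its own accuracy carries no overfitting bias. This stands for each criterion taken singly. It does not stand for the winner once it has been picked, and the only primary analysis named is a fitted five-variable model that the sponsor itself calls predictive.

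The SAP may contain internal validation. That cannot be checked, so the point is limited to what the protocol requires.

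Some stronger readings are tempting but not supported:
- A reader might infer that the model is meant to select patients for dose reduction. Section 5 raises dose reduction only as background, and no objective in section 6 mentions it.
- A reader might infer that the result will certainly be overstated. Optimism is an average; a single sample can fall either way.
- A reader might extend the point to the ultrasound objective in 6.2. No model is specified there, so it applies only if a multivariable model is fitted.
- A reader might treat the n=50 results as the main case. Section 7.5 makes by-arm fits conditional, and after the amendment two arms of 50 are no longer assured. A smaller second cohort would fare worse, but that is not the primary pooled analysis.

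**Conclusion.** The point holds as an expectation. If the protocol is followed as written, with nothing added in the SAP, a claim about predictive performance is expected to be too favourable. For the pooled analysis the size is modest to moderate: about 0.03 to 0.10 AUC for the five-variable model and about 0.02 to 0.06 for the best single criterion. For a five-variable fit in 50 patients it is about 0.06 to 0.18.

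These figures depend on an assumed Month 12 remission rate of 20% to 40%, assumed correlations and moderate association. With strong association the pooled optimism sits at the lower end. The protocol also does not say whether the indices enter as scores or as remission status; both codings were covered. The n=100 figures may be favourable to the plan, because a model that includes ultrasound loses patients from any center not selected for it.

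This is a recommended change rather than a flaw that invalidates the study.

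**What to change.** In section 7.7:
- Name one performance measure, for example AUC, on which the Month 6 criteria are compared.
- Report it with a bootstrap optimism correction (at least 500 resamples) that repeats the whole process in each resample: model fitting and the choice of the best criterion.
- Report how often each criterion is chosen across resamples.
- Base any statement on predictive ability on the corrected figures.
- Use penalised estimation, for example Firth, where resamples separate. This is a real possibility with few events and overlapping criteria.
- Apply the same to any multivariable ultrasound prediction model, and label by-cohort fits exploratory.

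Multiplying all coefficients by one shrinkage factor is not needed for this objective. It leaves the AUC and the order of the coefficients unchanged, so it cannot alter which criterion is named best.

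The cost is a paragraph of text and a short program, possibly through an extension to the SPSS package named in section 7.6. No new data or patients are needed. The downside is that reported performance will look less favourable.
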